### 5.1.2 Secondary Estimands

Secondary Objective 2.3.2.1: To compare proportions of participants treated with RPT/CFZ-containing regimens who experience favorable composite efficacy outcome at 65 weeks with Arm 2 (6-month SOC controls)	
Estimand description	Difference in proportion with favorable outcomes 65 weeks after initiation of TB therapy (PHZE+CFZ versus RHZE) among individuals aged $\geq 18$ years and with pulmonary TB without demonstrated isoniazid or rifampicin resistance.
Treatment	13-week Experimental Regimen: rifapentine/isoniazid/pyrazinamide/ethambutol (PHZE) + clofazimine (CFZ)  26-week Standard of Care: rifampicin/isoniazid/pyrazinamide/ethambutol (RHZE) followed by rifampicin/isoniazid (RH)
Target population	Analysis set
Individuals aged $\geq 18$ years with confirmed pulmonary TB without demonstrated isoniazid or rifampicin resistance who initiate TB therapy.	Efficacy set (All participants who are randomized to study treatment and are not late exclusions)
Variables	Outcome measure 3.2.1 A
Favorable outcome 65 weeks after initiation of TB therapy following evidence of cure at treatment completion where favorable outcome is defined by any one of the following:  
 
• Liquid culture negative at 65 weeks after TB therapy initiation
 
• No signs or symptoms of ongoing active TB and unable to produce a sputum specimen at 65 weeks after TB therapy initiation
 
• No signs or symptoms of ongoing active TB and a sputum specimen that is contaminated in two liquid cultures without evidence of TB at 65 weeks after TB therapy initiation
 
 Absence of cure at or after treatment completion is an unfavorable outcome.	Favorable clinical/bacteriologic outcome at the 65 week study visit.
Handling of intercurrent events	Handling of missing data
The following intercurrent events are relevant to the estimand.  1. Death except from violent or accidental cause (e.g., road traffic accident) Unfavorable outcome ( composite strategy )  2. Violent or accidental death Unevaluable outcome* ( hypothetical strategy )  3. Extension of treatment beyond the nominal duration due to clinically inadequate response Unfavorable outcome ( composite strategy )  4. New TB diagnosis due to a new strain of Mtb Unevaluable outcome* ( hypothetical strategy )	Participants lost to follow-up and culture negative at their last visit meet the definition of "unevaluable" and will be censored at the time of their last follow-up visit  Participants with a positive culture for Mtb when last seen, whether confirmed by a second sample or not, unless determined to have been re-infected will be considered to have an unfavorable outcome and the event time will be the visit when last seen.  Participants with a new TB diagnosis due to a new strain of Mtb will be censored at the time of their last follow-up visit.

5. Pregnancy during treatment resulting in discontinuation of initial therapy Unevaluable outcome* (hypothetical strategy)
 
6. Failure to complete treatment (except for 2 and 5 above) All follow-up through to 65 weeks will be used to determine the variable irrespective of duration of treatment (treatment policy strategy)
 
* See handling of missing data for imputation rules for unevaluable outcomes
	Participants who become pregnant during assigned active treatment and discontinue treatment will be censored at the time of treatment discontinuation.
Population-level summary measure	Analysis approach
Difference in cumulative probability of having a favorable clinical/bacteriologic outcome at 65 weeks after TB therapy initiation.	Difference in cumulative proportion of participants at 65 week visit together with 90% and 95% two-sided confidence intervals. We will use the Kaplan-Meier estimator and Greenwood's estimate for the standard error.

Secondary Objective 2.3.2.1: To compare proportions of participants treated with RPT/CFZ-containing regimens who experience favorable composite efficacy outcome at 65 weeks with Arm 2 (6-month SOC controls)	
Estimand description	Difference in proportion favorable outcomes 65 weeks after initiation of TB therapy (PHZE+CFZ versus RHZE) among individuals aged $\geq 18$ years and with pulmonary TB without demonstrated isoniazid or rifampicin resistance who complete TB treatment.
Treatment	13-week Experimental Regimen: rifapentine/isoniazid/pyrazinamide/ethambutol (PHZE) + clofazimine (CFZ)  26-week Standard of Care: rifampicin/isoniazid/pyrazinamide/ethambutol (RHZE) followed by rifampicin/isoniazid (RH)
Target population	Analysis set
Individuals aged $\geq 18$ years living with confirmed pulmonary TB without demonstrated isoniazid or rifampicin resistance who complete TB therapy.	Efficacy set (All participants who are randomized to study treatment and are not late exclusions)
Variables	Outcome measure 3.2.1B
Favorable outcome 65 weeks after initiation of TB therapy following evidence of cure at treatment completion where favorable outcome is defined by any one of the following:  
 
• Liquid culture negative at 65 weeks after TB therapy initiation
 
• No signs or symptoms of ongoing active TB and unable to produce a sputum specimen at 65 weeks after TB therapy initiation
 
• No signs or symptoms of ongoing active TB and a sputum specimen that is contaminated in two liquid cultures without evidence of TB at 65 weeks after TB therapy initiation
 
 Absence of cure at or after treatment completion is an unfavorable outcome.	Favorable clinical/bacteriologic outcome at the 65 week study visit.
Handling of intercurrent events	Handling of missing data
The following intercurrent events are relevant to the estimand:  Intercurrent events that occur during therapy: 
 
1. Death except from violent or accidental cause (e.g., road traffic accident) Unfavorable outcome* (Composite strategy)
 
2. Violent or accidental death Unevaluable outcome* (Composite strategy)
 
3. A re-start of therapy following <math>\geq 30</math> consecutive days without therapy Unfavorable outcome (Composite strategy)
 
4. A change in at least one drug in treatment regimen for any reason except re-infection, pregnancy, or temporary drug challenge. Unfavorable outcome (Composite strategy)
 
	Participants lost to follow-up during the treatment phase are considered to have an unfavorable outcome (regardless of TB culture result at the last available visit) and the event time is the time of the last visit.  Participants failing to complete treatment and not assessable at the end of the follow-up period are considered to have an unfavorable outcome and the event time is the time of the last treatment dose received.  Participants receiving an extension of treatment, re-start of treatment, or change in treatment (see full definition B of unfavorable outcome) are considered to have an unfavorable outcome and the event time is the time of the treatment modification.


5. Pregnancy during treatment resulting in discontinuation of initial therapy Unevaluable outcome* (Composite strategy)
 
Intercurrent events that occur after adequate** completion of therapy:
 
6. Death except from violent or accidental cause (e.g., road traffic accident) Unfavorable outcome (Composite strategy)
 
7. Violent or accidental death Unevaluable outcome* (Hypothetical strategy)
 
8. Extension of treatment beyond the nominal duration except to make up missed doses Unfavorable outcome (Composite strategy)
 
9. New TB diagnosis due to a new strain of Mtb Unevaluable outcome* (Hypothetical strategy)
	
Participants lost to follow-up after the treatment phase with their last available TB culture being negative are considered unevaluable and are censored at the time of the last visit.
 
Participants who experience violent or accidental death are considered to have an unevaluable outcome and will be censored at the time of their last follow-up visit.
 
Participants reinfected with a new strain of Mtb are considered to have an unevaluable outcome and will be censored at the time of their last follow-up visit.
 
Participants who become pregnant during their assigned active treatment and who stop their assigned treatment are considered to have an unevaluable outcome and will be censored at the time of the last treatment dose received.

* See handling of missing data for imputation rules for unevaluable outcomes
 
Population-level summary measure
 
Difference in cumulative probability of having a favorable clinical/bacteriologic outcome at 65 weeks after TB therapy initiation .
	
Analysis approach
 
Difference in cumulative proportion of participants at 65 week visit together with 90% and 95% two-sided confidence intervals. We will use the Kaplan-Meier estimator and Greenwood's estimate for the standard error.

\*\* Adequate completion of therapy is determined by the following definitions:

Definitions of Adequate Treatment Within 3-month Regimen (Arm 1 in the setting of this trial)

- Taken a total of at least 56 doses of allocated intensive phase treatment within 70 days of starting treatment
- AND taken at least 28 doses of continuation phase treatment within 49 days (7 weeks) of completion of the intensive phase
- AND missed no more than 21 doses of medication overall.

Definitions of Adequate Treatment within 6-month Regimen (Arm 2 in the setting of this trial)

- Taken a total of at least 56 doses of allocated intensive phase treatment within 70 days of starting treatment
- AND taken at least 100 doses of continuation phase treatment within 154 days (22 weeks) of completion of the intensive phase
- AND missed no more than 42 doses of medication overall.

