## 2 Study Overview

### 2.1 Overview of Study Design

A5362 is an open-label, randomized phase IIc study to evaluate whether a 3-month regimen of rifapentine/isoniazid/pyrazinamide/ethambutol (PHZE) with clofazimine (CFZ) dosed as 100 mg daily with a 2-week 300 mg daily loading dose is superior to the standard of care (SOC) 6-month regimen of rifampin/isoniazid/pyrazinamide/ethambutol (RHZE) for DS-TB with respect to (1) early bacteriologic efficacy defined as time to culture conversion by 12 weeks post-randomization and (2) safety over 65 weeks.

Participants will be randomized to one of three treatment arms; Arm 1 with treatment for 13 weeks (including a 2-week CFZ loading dose of 300 mg daily; Arm 2 with treatment for 26 weeks; or Arm C with treatment for 4 weeks with an experimental regimen and the remaining 22 weeks with SOC (PK subgroup)).

- Arm 1 (Experimental): PHZE + CFZ 300 mg once daily for 2 weeks, PHZE + CFZ 100 mg once daily for 6 weeks; then PHZ + CFZ 100 mg once daily for 5 weeks
- Arm 2 (SOC): RHZE for 8 weeks; then RH for 18 weeks
- Arm C (PK subgroup): PHZE + CFZ 100 mg once daily for 4 weeks; then on study, off study medications and treated according to SOC (RHZE for 4 weeks; RH for 18 weeks)

We will follow all participants in Arms 1, 2, and C from randomization to week 65 for the primary and secondary objectives. Protocol v2.0 LOA #1 also includes extended follow-up for some participants corresponding to new exploratory objectives which will be detailed in a separate SAP.

Participants who consent to intensive PK sampling visits will be randomized to Arms 1, 2, or C in a 2:1:1 ratio, respectively, while participants who do not consent to intensive PK sampling will be

randomized only to Arms 1 or 2 in a 2:1 ratio, respectively. We will stratify randomization based on HIV status and the presence of advanced disease as determined by chest X-ray. We will balance randomization by institution.

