#### Unevaluable Outcome

- Participants lost to follow-up during treatment or post-treatment follow-up with their last culture being negative for *Mtb*.
- Violent or accidental death.
- Participants with recurrent TB due to a new strain of *Mtb* confirmed by conventional molecular genotyping (as defined by MIRU and IS6110 typing).
- Women who become pregnant during their assigned active treatment and stop their assigned treatment.

Favorable, unfavorable, and unevaluable composite outcomes (B) are defined as follows:

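### SAP 5.1.2 classes new-strain TB as unevaluable but censors it at the last follow-up visit, which can fall after the reinfection and its retreatment

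*SAP*

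**What the plan says.** The SAP's definition of the clinical/bacteriologic outcome (3.2.1 A) lists as unevaluable "Participants with recurrent TB due to a new strain of" Mtb confirmed by genotyping. The composite outcome (3.2.1 B) does the same for reinfection.

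Table A in 5.1.2 lists "New TB diagnosis due to a new strain of" Mtb as an intercurrent event that is unevaluable under a hypothetical strategy. A footnote sends the reader to the missing-data column for the handling of unevaluable outcomes. That column says: "Participants with a new TB diagnosis due to a new strain of" Mtb "will be censored at the time of their last follow-up visit". In table B the hypothetical label appears among the events after adequate completion of therapy, and the missing-data column says that reinfected participants "are considered to have an unevaluable outcome and will be censored at the time of their last follow-up visit".

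Pregnancy that leads to stopping treatment is also unevaluable under a hypothetical strategy in table A. Its rule is different: "Participants who become pregnant during assigned active treatment and discontinue treatment will be censored at the time of treatment discontinuation".

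On length of follow-up, SAP 2.1 states: "We will follow all participants in Arms 1, 2, and C from randomization to week 65 for the primary and secondary objectives". Letter of Amendment #1 (Schema, Design and Duration) keeps Arm 1 participants with diagnosed recurrence on study for outcome determination after referral to standard-of-care treatment, with a duration of 65 weeks. SAP 5.1.3.9 defines recurrence without requiring a matching strain, so reinfection is included.

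**The concern.** A hypothetical strategy asks how the original infection would have turned out had the reinfection not happened. Follow-up during and after a second course of TB treatment does not answer that question. If the participant stays in the risk set until week 65, the estimator uses that follow-up as event-free time.

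At stake are the week-65 proportions for 3.2.1 A and B and the difference between the arms. These matter for a trial that closed early because of treatment failure and recurrence. There is also a loose end: both tables count non-violent death as unfavorable, and neither says whether a death after a new-strain diagnosis still counts once the participant has been classed as unevaluable.

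**Working it through.** **Where the censoring visit falls.** The unevaluable categories for A, and their censoring times, compare as follows.

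- Loss to follow-up while culture-negative: the last visit, which necessarily comes before the missing period.
- Pregnancy with treatment stopped: the intercurrent event itself.
- New strain: the last follow-up visit, which comes after the intercurrent event for anyone who stays on study.

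Violent death has a stated rule only in table B, again the last visit, which precedes the event. New-strain TB is therefore the one category where the wording can place censoring after the event. No other rule closes the gap. Absence of cure requires a strain matched to the initial isolate. Definition B exempts drug changes made because of reinfection. The only stated bar to a favorable classification is a prior unfavorable outcome.

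**Formula.** The SAP gives no reinfection rate and no figure for this estimand, so there is nothing to reproduce. Let N be the arm size, d1 the unfavorable events up to the reinfection time, d2 those after it, n1 = N − d1, and k the number reinfected. There is no other censoring before week 65.

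- Rule as written (censored at week 65): S = (N − d1 − d2)/N. This does not depend on k; each reinfected participant has the weight of a favorable completer.
- Censored at reinfection: S = (n1/N) × (n1 − k − d2)/(n1 − k).
- Understatement of the unfavorable proportion = d2 × k / [N × (n1 − k)].

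**Per-arm size.** N = 110 is the planned Arm 1 size (SAP 2.4). The event counts (12 and 25, evenly spaced over weeks 13 to 60) and reinfection at week 34 are assumptions. Even spacing gives d1 = 5, d2 = 7, n1 = 105 for 12 events, and d1 = 11, d2 = 14, n1 = 99 for 25.

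| k | 12 events | 25 events |
|---|---|---|
| 1 | 7 × 1/(110 × 104) = 0.06 points | 14 × 1/(110 × 98) = 0.13 points |
| 5 | 7 × 5/(110 × 100) = 0.32 | 14 × 5/(110 × 94) = 0.68 |
| 8 | 7 × 8/(110 × 97) = 0.52 | 14 × 8/(110 × 91) = 1.12 |

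The unfavorable proportion under the written rule is 12/110 = 10.9% or 25/110 = 22.7%. The standard errors, √[p(1 − p)/110], are 3.0 and 4.0 points. If d2 = 0 the shift is zero.

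**Between-arm difference.** Assume Arm 1 has N = 110 and 22 events (d1 = 10, d2 = 12, n1 = 100), and Arm 2 has N = 55 (planned) and 4 events at weeks 26, 34, 42 and 52 (d1 = 2, d2 = 2, n1 = 53), with reinfection again at week 34. The shift in the favorable difference, Arm 1 minus Arm 2, is as follows.

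- 2 v 1 reinfections: 24/(110 × 98) − 2/(55 × 52) = 0.22 − 0.07 = +0.15 points.
- 4 v 2: 48/(110 × 96) − 4/(55 × 51) = 0.45 − 0.14 = +0.31 points.
- 1 v 4: 12/(110 × 99) − 8/(55 × 49) = 0.11 − 0.30 = −0.19 points.

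The per-arm standard errors are 3.81 and 3.50 points, so that of the difference is √(3.81² + 3.50²), about 5.2 points.

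**The case against.** The strongest reply is that the phrase was meant as the last usable visit. In the same column it serves for loss to follow-up, where it can mean nothing else. The reinfection sentence also directly follows the rule for participants culture-positive when last seen, which excepts reinfection; it could be read as completing that exception for someone whose last visit showed the new strain. The hypothetical strategy favors this reading too. It may well be the intent, but the text does not say so. The pregnancy rule names the event where the event is meant, and a programmer working from the sentence would take the last visit on study. The Analysis Implementation Plan may settle the coding, but it is not available here and cannot be relied on to override a rule stated in the SAP.

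Two stronger conclusions are tempting, and the documents do not support them. One is that reinfected participants are counted as favorable. They are not: both definitions keep them unevaluable, and only their Kaplan-Meier weight equals that of a completer. The other is that the bias always runs one way. The summary measure is the between-arm difference, and its shift takes the sign of the imbalance, as the third case above shows. Even within an arm the shift is zero if no event follows the reinfection, and a later non-violent death counted as unfavorable would move the estimate the other way.

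It is also fair to say that the size cannot change a conclusion. These are secondary outcomes reported by estimation; SAP 2.3 reserves the formal test for the primary efficacy objective.

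**Conclusion.** The point holds as a mismatch between the stated strategy and the censoring rule in both 5.1.2 tables. It applies only to participants who remain on study after a new-strain diagnosis; someone who leaves at diagnosis is censored there under either rule. Under the assumptions above, the per-arm unfavorable proportion at week 65 is understated by about 0.06 to 0.13 points for 1 reinfection, 0.3 to 0.7 for 5 and 0.5 to 1.1 for 8. The difference moves by a few tenths of a point in either direction. Both are small beside the sampling error.

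The reinfection counts and times and the event counts are assumptions, and the arm sizes are planned ones that may not have been reached, because accrual closed early. Extra Arm 1 contacts under Letter of Amendment #1, with none added in Arm 2, could make detection of reinfection differ by arm; the documents give no data on this. This is a minor correction, worth making because it is cheap and removes a choice that would otherwise fall to the programmer.

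**What to change.** In the missing-data column of both tables, replace the new-strain sentence with one that censors at the reinfection: either the visit of the first culture that yields the new strain, or the last evaluable visit before it. The documents do not decide between the two, so choose one and use it in both tables. Add that data after that point, including later deaths, are not used for this outcome.

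The cost is one sentence per table and a matching line in the Analysis Implementation Plan. No new data are needed, because genotyping is already planned.

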### 5.1.3 Secondary Objectives

#### 5.1.3.1 Tolerability (Objective 2.3.2.2; Outcome Measure 3.2.2)

We will compare the proportion of participants who permanently and prematurely discontinue study treatment for any reason between arms in the start treatment/not late exclusion set.

Permanent and premature discontinuation of study treatment is defined as not having completed an adequate dose of treatment as defined in Section 3.2.1. We will exclude participants who discontinued due to violent or accidental death, natural disaster, or administrative censoring (e.g. site closure), from the analysis. The difference in proportions will be estimated using binomial proportions, and we will provide exact 95% confidence intervals.

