#### Definitions of Adequate Treatment Within 3-month Regimen (Arm 1)

- Taken a total of at least 56 doses of allocated intensive phase treatment within 70 days of starting treatment
- AND taken at least 28 doses of continuation phase treatment within 49 days (7 weeks) of completion of the intensive phase
- AND missed no more than 21 doses of medication overall.

Definitions of Adequate Treatment within 6-month Regimen (Arm 2)

- Taken a total of at least 56 doses of allocated intensive phase treatment within 70 days of starting treatment
- AND taken at least 100 doses of continuation phase treatment within 154 days (22 weeks) of completion of the intensive phase
- AND missed no more than 42 doses of medication overall.

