3.2.2 Tolerability

Proportion with premature discontinuation through 65 weeks, defined as discontinuation other than due to violent death, natural disaster, or administrative censoring.

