
 
1. Persistent clinical disease and extension of treatment Observations will be used to determine the variable (treatment policy strategy)
 
2. Premature treatment discontinuation Observations will be used to determine the variable (treatment policy strategy)
 
3. Premature treatment discontinuation due to suspected TB treatment failure or TB recurrence or poor treatment response. Observations will be used to determine the variable (treatment policy strategy)
 
	Participants who discontinue follow-up before week 65 will have their outcome determined based on data available until the time of discontinuation (i.e., missing observations after discontinuation that would be relevant to the variable are considered missing completely at random).  Sensitivity analyses will consider participants who discontinue follow-up before week 65 as having at least one Grade 3 or higher adverse event that is at least a one-grade increase from baseline.
Population-level summary measure	Analysis approach
Probability of having at least one Grade 3 or higher AE that is at least one-grade increase from baseline at any time during the 65 weeks after treatment initiation.	We will compare the cumulative proportion of participants experiencing a Grade 3 or higher AE that is at least one-grade increase from baseline at any time during the 65-week study period between Arm 1 and Arm 2 using the Kaplan-Meier estimator at week 65. Participants who have not experienced an event will be censored at the last completed study visit. For participants who experience more than one event, we will use the time of the first occurrence as the time of event. We will present the point estimate and 90% two-sided confidence intervals for the difference in cumulative proportions.

Supplemental Analyses:

As supplementary analyses, we will also estimate the Kaplan-Meier proportions and confidence intervals for the outcome measure up to week 13, and up to week 26. These time horizons correspond to the end of treatment for Arm 1, and Arm 2, respectively.

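### The tolerability analysis compares completion of a 13-week course with completion of a 26-week course; a supplementary week-13 estimate is needed to show how well the drugs are tolerated over equal exposure

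*SAP*

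**What the plan says.** SAP section 2.1 sets the courses: "Arm 1 with treatment for 13 weeks" and "Arm 2 with treatment for 26 weeks". Outcome 3.2.2 is "Proportion with premature discontinuation through 65 weeks, defined as discontinuation other than due to violent death, natural disaster, or administrative censoring".

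Section 5.1.3.1 makes this operational as a status: "Permanent and premature discontinuation of study treatment is defined as not having completed an adequate dose of treatment as defined in Section 3.2.1". The adequacy rules in 3.2.1 differ by arm. The intensive-phase rule is shared ("Taken a total of at least 56 doses of allocated intensive phase treatment within 70 days of starting treatment"). The continuation-phase minimum is 28 doses within 49 days in Arm 1 and 100 doses within 154 days in Arm 2, and at most 21 and 42 missed doses are allowed. On the analysis, 5.1.3.1 says: "The difference in proportions will be estimated using binomial proportions, and we will provide exact 95% confidence intervals". The population is the start treatment/not late exclusion set. Section 6.7 lists the same difference for 3.2.2, and 6.4 adds a summary of reasons for stopping.

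For the primary safety outcome, section 5.1.1 adds Kaplan-Meier estimates at weeks 13 and 26, and explains: "These time horizons correspond to the end of treatment for Arm 1, and Arm 2, respectively". Section 5.1.3.5 does the same for SAEs, and 5.1.3.2 compares QTcF change at weeks 2, 8 and 13 in both arms. The SAP specifies no such horizon, time-to-event curve or rate for discontinuation.

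**The concern.** Section 2.2 hypothesises acceptable safety and tolerability for Arm 1, and section 2.1 names regimen discontinuation among the important secondary analyses. A reader will therefore take the 5.1.3.1 difference as evidence on how well the clofazimine/rifapentine combination is tolerated.

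That difference combines two things: how readily participants stop the drugs, and how long they are asked to take them. Every Arm 2 stop after week 13 falls in a period when the nominal Arm 1 course is over. Equal tolerability week by week would therefore appear as an Arm 1 advantage, and a real excess of early stopping in Arm 1 could appear as no difference. The horizons that would separate the two are planned for AEs and SAEs, but not for the outcome that carries the name tolerability.

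**Working it through.** **No figure to reproduce.** The documents give no rate, power or precision for tolerability. Arm 2 whole-course discontinuation (p2) is therefore assumed at 5%, 10% and 20%.

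**Inputs from the SAP.** Course lengths 13 and 26 weeks (2.1); adequate-dose minimums 56 + 28 = 84 and 56 + 100 = 156 doses (3.2.1); planned arm sizes 110 and 55 (2.4).

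**Constant weekly hazard.** Arm 2 hazard h = −ln(1 − p2)/26; cumulative proportion by week 13 = 1 − exp(−13h). For p2 = 10%: h = 0.10536/26 = 0.00405, and 1 − exp(−0.0527) = 5.1%. If the Arm 1 hazard is 2h, its whole-course proportion is 1 − exp(−26h) = p2.

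| Assumed Arm 2 whole course | Planned difference (Arm 1 − Arm 2), equal hazards | Planned difference, Arm 1 hazard doubled | Week-13 proportions, Arm 1 hazard doubled | Week-13 difference |
|---|---|---|---|---|
| 5% | 2.5% − 5% = −2.5 points | 0 | 5.0% v 2.5% | +2.5 points |
| 10% | 5.1% − 10% = −4.9 points | 0 | 10.0% v 5.1% | +4.9 points |
| 20% | 10.6% − 20% = −9.4 points | 0 | 20.0% v 10.6% | +9.4 points |

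**Hazard ratio that shows no planned difference.**
- Nominal durations: 26/13 = 2.00.
- Adequate-dose minimums, assuming dosing seven days a week: 84/7 = 12.0 weeks and 156/7 = 22.3 weeks, ratio 1.86.
- Longest windows allowed by the adequacy rules: 70 + 49 = 119 days and 70 + 154 = 224 days, ratio 1.88.
- Hazard not constant: if a share f of Arm 2 stops falls by week 13, the average hazard ratio over weeks 0 to 13 that equalises the planned proportions is ln(1 − p2)/ln(1 − f·p2). At p2 = 10%, f = 60%, 70%, 80% and 90% give 1.70, 1.45, 1.26 and 1.12; f = 50% gives 2.05. A later pattern gives more.

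**Precision at week 13** (110 v 55, doubled hazard, normal approximation, two-sided 0.05). Power is about 9%, 16% and 32% for p2 = 5%, 10% and 20%. At p2 = 10%, expected events are 110 × 0.10 = 11 and 55 × 0.0513 = 2.8. The standard error is √(0.10 × 0.90/110 + 0.0513 × 0.9487/55) = 0.0413, so the 95% interval is about 4.9 ± 8.1 points, −3.2 to 13.0. With so few events the approximation is rough, and early closure to accrual makes it worse.

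**The case against.** The strongest reply is that completing the assigned course is the objective. Objective 2.3.2.2 concerns premature discontinuation of the regimen, and duration is part of each regimen. In a shortening trial, fewer weeks in which to stop is part of the benefit under test. This stands. A reader might infer that the planned comparison is biased or invalid; the documents do not support that.

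Three further replies also stand.
- The event in 5.1.3.1 is a status, not a dated stop. The intensive-phase rule is the same in both arms, and a participant who takes dose 56 after day 70 fails without stopping. A constant stopping hazard only approximates this event, and a week-13 analysis needs its own dated definition.
- The adequacy rules give Arm 1 up to 119 days, so some participants may still be making up doses at week 13.
- Common-time evidence on the drugs is planned for AEs, SAEs and QTcF. Only discontinuation itself lacks it.

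Low power is a weaker reply. Section 2.3 treats every objective except primary efficacy as estimation with confidence intervals, and the SAP's own safety table (section 2.4) includes scenarios with 13% and 36% power. A wide interval around the equal-exposure contrast is still information that the course-completion difference does not give.

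**Conclusion.** The point holds as a gap, not an error. The planned difference correctly estimates completion of the assigned course. It does not estimate tolerability over equal exposure, and the SAP specifies no analysis of discontinuation that does.

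Size depends on assumed rates. With 10% in Arm 2 and constant hazards, duration alone gives Arm 1 a 4.9-point advantage (2.5 to 9.4 points for 5% to 20%). A weekly rate about 1.9 to 2 times higher in Arm 1 would show no difference. The hidden ratio falls to about 1.7 to 1.1 if 60% to 90% of Arm 2 stops come by week 13, and can exceed 2 if they come late.

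Two other stronger readings are tempting and not supported. One is that the outcome has no common window: 3.2.2 states "Proportion with premature discontinuation through 65 weeks" for both arms, although that window does not equalise time on treatment. The other is that twofold is a ceiling: it is only the constant-hazard value from nominal durations.

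The outcome carries no margin or decision rule, so the consequence lies in interpretation. The SAP leaves detailed table outlines to the Analysis Implementation Plan, which is not among the documents; a time-to-discontinuation display there would narrow the gap.

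**What to change.** In 5.1.3.1, keep the planned proportion and describe it as completion of the assigned course. Add a supplementary analysis parallel to the one for primary safety: the Kaplan-Meier cumulative proportion with permanent discontinuation of assigned treatment by week 13 in each arm, with the difference and 95% CI, in the same analysis set. Specify that:
- the event is dated by the last dose taken, with a note on how this fits the visit-week convention of section 4.1;
- one stopping rule applies to both arms, separate from the arm-specific adequate-dose status;
- Arm 1 participants who have completed the course, or are still making up doses at week 13, are event-free at that time;
- violent or accidental death, natural disaster and administrative closure are censored.

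List it in 6.7, and cite it beside the completion result in any statement on how well the drugs are tolerated.

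The cost is SAP wording and one analysis. Last-dose timing is already needed for outcome 3.2.1 B, so no new data are required. The price is few Arm 2 events and a wide interval.

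Separately, Letter of Amendment #1 (item 3, Section SCHEMA, REGIMEN) gives Arm 1 participants on treatment as of 16 June 2023 a total of 26 weeks of study treatment, while SAP 3.2.1 defines Arm 1 adequate treatment for the 3-month regimen only. These passages must be reconciled for this outcome. The week-13 estimate is largely unaffected by how that is settled.
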